3.2.8 Follow-Up of Adverse Events

Patients should be asked to specifically describe any signs, symptoms, or AEs (regardless of relationship to therapy) they may notice prior to the start of the study or thereafter. At a minimum, patients should be asked to report AEs at each visit to the study site. Conditions that the patient experienced prior to informed consent should be recorded in the medical history section of the eCRF.

Follow up of an “overdose” should include continued monitoring of all protocol-specific laboratory results, including chemistry and hematology, using the protocol-specified time points for laboratory tests, with the exception that an additional full series of chemistry, hematology, and coagulation tests, a full physical examination, vital signs, and ECG should be conducted within 24 hours of investigator awareness of that the patient received an “overdose”. Following this additional ad hoc re-evaluation, the investigator should use his or her medical judgment in deciding whether additional supplemental medical treatment is needed to treat adverse medical consequences of the overdose. Also after the ad hoc re-evaluation, the investigator should use his or her medical judgment in deciding whether additional supplemental monitoring is needed to track resolution of any AEs or other abnormal findings to the point of resolution to a CTCAE Grade 1 AE.

3.2.9 Clinical Laboratory Evaluations

Clinical laboratory tests, fasting or post meal, will be reviewed for results of potential clinical significance at all time points throughout the study. The abnormality will be graded under Investigation category of CTCAE version 4.03 independent of clinical significance. The investigator will evaluate any change in laboratory values.

Hematology testing will include the following parameters: hemoglobin, hematocrit, red blood cell count, white blood cell count with differential, platelet count, coagulation, including prothrombin time, activated partial thromboplastin time (aPTT), and International Normalized Ratio.

Serum chemistry testing will include the following parameters: blood urea nitrogen, creatinine, AST, ALT, gamma-glutamyl transpeptidase, total bilirubin (including direct fraction if total bilirubin is abnormal), lipase, amylase, total protein, albumin, alkaline phosphatase, sodium, potassium, calcium, magnesium, random blood glucose, lactate dehydrogenase (LDH), creatine kinase MB fraction.

Urinalysis (glucose, protein, occult blood test) will be performed by dipstick method, and in the event of abnormal dipstick results, additional test may be required.

The following information will be captured for blood sample collection in each patient’s eCRF:

- Subject number
- Time and date of dose administration
- Time and date of patient’s most recent ingestion of food prior to dose administration

3.2.10 Vital Signs, Physical Findings and Other Safety Assessments

Vital signs measurements will include pulse rate and systolic and diastolic blood pressure in a seated position of at least 5 minutes.

Physical examinations will be performed. A skin assessment will be conducted per the standard procedure of the site. For skin lesions, photograph with an adjacent ruler to indicate size will be obtained, if needed.

ECG are to be 12-lead. Vital signs measurements should be performed prior to the ECG.

To assess QTc intervals, 12-lead ECGs in triplicate will be obtained at 3.5 ± 0.5 hours after taking study medications on C1D1 and C2D1. The patient should be in seating position for 5 minutes before the 1st ECG is obtained, followed by 2nd and 3rd ECGs with 5 ± 2 minutes between ECG measurements.

3.3 Pharmacokinetics

Pharmacokinetic sampling for population PK will be performed as detailed in Table 4: of Appendix A.

Blood samples (2 mL) will be drawn into evacuated tubes containing dipotassium ethylene diaminetetra acetic acid. Each sample will be inverted several times and then placed immediately into an ice bath. Within 30 minutes of sampling, tubes must be centrifuged at $1,000 \times g$ at 4°C for 5 minutes. Plasma fractions will then be transferred in 200 μL aliquots into 2 cryogenic vials. The cryogenic vials will be labeled as A or B, plus the unique subject number, collection time, and date before being frozen. Samples will be placed and stored at -70°C within 30 minutes of transfer to the cryogenic vial. The original sample for PK analysis (A) and the duplicate sample (B) will be stored at -70°C . For each patient participating PK study, PK (A) samples from Cycles 1 and 2 could be shipped together after Cycle 2 Day 1. The site could also ship all samples (Cycles 1 to 6) from each individual patients in one shipment. Samples from several patients could be batched together for shipment as well. The shipment for back-up samples (B) would be handled similarly. PK samples (A) and samples (B) will be shipped to [REDACTED].

Details of sample collection, handling, storage, and transport methodology will be provided to the investigator in the laboratory manual.

The following information will be captured for blood sample collection in each patient's eCRF:

- Subject number
- Time and date of dose administration (as well as time and date of previous dose administration for PK samples collected from Cycle 2 onwards)
- Time and date of each blood sample collected for pharmacokinetic analysis
- Time and date of patient's most recent ingestion of food prior to dose administration

3.4 Blood Volume

The total blood volume for each patient to be collected at screening is approximately 20 mL. Blood volume collected for safety tests on Days 1, 8, 15, and 22 of Cycle 1 will be approximately 30 mL. Assuming each patients would receive up to 6 Cycles of treatment, subsequent cycles will have blood collections for safety tests on Days 1 and 15 of Cycle 2 then Day 1 of Cycles 3 to 6. The total blood collection volume for Cycles 2 to 6 will be approximately 58.5 mL. The total blood collection volume for EoT will be approximately 6 mL for safety tests. For patients participating in PK study, blood volume for PK would be 30 mL for Cycle 1, 15 mL for Cycle 2 and 2 mL pre-dose on Day 1 of Cycles 3 to 6. For patients receiving treatment Cycle 7 and beyond, there will be no PK blood sample except for 10.5 mL blood for safety tests. The assumptions are listed in Table 2 and Table 3.

Table 2: Screening Cycle 1

	Number of Samples	Sample Volume (mL)	Total Volume (mL)
Hematology	5	2	10
Serum chemistry	5	4	20
Coagulation	3	4.5	13.5
Hepatitis B virus tests	1	2	2
Hepatitis C virus tests	1	4	4
Total (excluding PK)			49.5
Pharmacokinetics	10	3 ^a	30
Total (PK participating patients)			79.5

PK: pharmacokinetic

^a The sample volume of 3 mL includes 1 mL of blood needed for flushing the catheter tubing prior to a sample collection.

Table 3: Cycles 2 to 6

	Number of Samples	Sample Volume (mL)	Total Volume (mL)
Hematology	6	2	12
Serum chemistry	6	4	24
Coagulation	5	4.5	22.5
Total (excluding PK)			58.5
Pharmacokinetics cycle 2 day 1	5	3 ^a	15
Pharmacokinetics cycles 3-6 day 1	4	2	8
Total (PK participating patients)			81.5

PK: pharmacokinetic

^a The sample volume of 3 mL includes 1 mL of blood needed for flushing the catheter tubing prior to a sample collection.

3.5 Independent Review

3.5.1 Data Safety Monitoring Board

A DSMB has been established to monitor the safety observed during the conduct of this study. For all patients, weekly safety laboratory tests should be obtained during the first 28 days and closely monitored for safety signals, especially the neutropenia and transaminase elevation. DSMB consists of 3 oncologists who are experienced in treating patients with PTCL and are not associated with this study. They are assisted by one DSMB statistician.

DSMB convenes at planned intervals based on patient accrual (see Section 2.6). Upon reviewing cumulative safety data from the study and taking into consideration of state-of-the-art medical practice, they will advise sponsor for treatment modification including dose adjustment, AE management, and continuation of treatment.

3.5.2 Independent Radiology Review

To ensure consistent radiology method is applied to assess disease response across the entire study, designated radiologists will review sequential imaging studies of individual patients. They will assign response outcome including best response, dates of initial response and progression when applicable, based on Cheson Criteria. They will be blinded to the local radiology findings. Should discrepancy between assessments by independent radiologist and site occur, a 2nd independent radiologist will adjudicate by selecting assessment from either site or 1st independent radiologist for final analysis.

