2.6 Study Procedures Overview

Patients may be treated in this study as long as they receive clinical benefit (stable disease or a response) in the absence of unacceptable toxicity. Disease progression would be determined by investigators based on local radiology findings and clinical judgement. No independent radiology review is required prior to designation of PD and treatment discontinuation. Independent Radiology Review and Independent Overall Efficacy Review will be performed for final efficacy analyses at the completion of this study.

To ensure patient safety, a data safety monitoring board (DSMB) will convene to review the cumulative safety profiles of study patients at following milestones: first 6 patients completing at least 1 cycle, 12, 18, 30 patients have been treated for at least 1 cycle and at end of treatment Phase of the study. Based on the observed safety, dose and regimen of ongoing treatment may be modified as needed. For all patients, weekly safety laboratory tests will be obtained during the first 28 days and closely monitored for safety signals, especially for neutropenia and transaminase elevation.

It is estimated that each patient will be on study for up to 42 months after enrollment. Assuming that 24 months are needed to meet accrual target, the study period would be of 66 months to allow efficacy and safety determination. After study drug is discontinued, patients will be followed as described in Sections 2.6.4 and 2.6.5.

Patients will be screened by the study site investigator prior to entry into the study. Patients will receive a detailed explanation of the study design, and the potential risk/benefit of treatment will be disclosed to patients prior to the screening process. Only eligible and consenting patients will be enrolled into the study. Local histopathology report could be used to consent patient. Central pathology review will be completed before efficacy analysis. The investigator will maintain a pre-screening log to record all patients prior to screening.

Similarly, local radiology reports on disease status will guide investigator's decision on study treatment, including discontinuation. At end of the study, tumor response of each patient will be reviewed by independent radiologists and oncologists in a blinded fashion to obtain best response, dates of response and progression. The data from independent and local assessment will be analyzed in parallel in final study report.

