3.0 STUDY ASSESSMENTS

3.1 Efficacy

3.1.1 Primary Efficacy Endpoint

The primary efficacy endpoint is to establish the ORR, defined as the proportion of patients with tumor size reduction of a predefined amount and for a minimum time period, evaluated by using the revised criteria for response assessment in lymphoma [[Cheson 2014](#)] (see Section 9.4).

Tumor assessments will be performed by imaging modalities. CT, magnetic resonance imaging, or PET scanning may be used to evaluate lesions in the neck, chest, abdomen, and pelvis; and as a baseline evaluation for patients who may have brain metastases. The PET-CT is encouraged to be performed from baseline. However, when CT is the routine method to monitor patients according to hospital standard of care, PET-CT is not required. Evaluation of nodal lesion and extranodal lesion will be performed according to the revised criteria for response assessment in lymphoma [[Cheson 2014](#)] (see Section 9.4). Skin lesions are non-target lesions. Their response will be assessed according to mSWAT, and contribute to overall response determination.

Tumor response based on imaging studies will be confirmed with central review by independent radiologists at end of study prior to final efficacy analysis. The dates of PR, CR and PD will be assessed as applicable. Initial review will be performed by one independent radiologist. If the results differ from those reported by the investigators based on local radiology findings, a second independent radiologist will be asked to adjudicate by way of assigning the final disease response to the determination made by either the investigators or independent radiologist. The overall efficacy review will be done by independent oncologist for final efficacy analysis.

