3.5.4 Independent Overall Efficacy Review

To ensure consistent overall efficacy review method is applied to assess disease response across the entire study, designated independent oncologists will review sequential clinical data of individual patients including radiological assessment provided by the independent radiological review. They will assign response outcome including best response, dates of initial response and progression when applicable, based on Cheson Criteria 2014.

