5.9 Efficacy Analysis

The efficacy endpoints are the following:

Primary Endpoint:

- ORR(CR + PR)

Secondary Endpoint:

- ORR by disease subtype (see Section 2.5.1)
- Median duration of PFS
- Median DOR

Exploratory Endpoint

- Median duration of OS

Response rate endpoints (ORR and ORR by disease subtype) will be summarized by number and percentage of patients meeting the definition of ORR along with the corresponding exact 95% CI. Tumor response as assessed by imaging studies will be adjudicated by independent radiology reviewers. Tumor lesions, such as skin lesion, that cannot be monitored by imaging studies will be determined by independent oncology reviewers and contributed to overall disease response assessment. Both investigators reported and independently adjudicated outcomes will be reported. Primary analysis will be based on results from imaging studies and clinical data confirmed by Independent Central Review. Results from investigator assessment will also be reported. In addition, the ORR will be analyzed according to histology subtypes of PTCL. The subtypes reported by Central pathology review for each patient will be used for such analysis.

Time-to event endpoints (PFS, DOR, and OS) for entire study population will be summarized by Kaplan-Meier methods (median, 95% CI, number of events, number censored and Kaplan-Meier figures).

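### Adjudication between the first independent radiologist and the site can only keep the blinded reading or substitute the site's, and masking of the adjudicator to source is not stated

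*Combined protocol and SAP*

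**What the plan says.** Section 3.1.1 has one independent radiologist read first. The trigger for a second is disagreement with the site: "If the results differ from those reported by the investigators based on local radiology findings". The second radiologist then settles the matter by "assigning the final disease response to the determination made by either the investigators or independent radiologist". Section 3.5.2 repeats the rule: "a 2nd independent radiologist will adjudicate by selecting assessment from either site or 1st independent radiologist for final analysis". Neither section offers a third outcome.

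The settled radiology result goes to independent oncologists. Under 3.5.4 they assign the overall response from sequential clinical data, "including radiological assessment provided by the independent radiological review". Section 5.9 then states: "Primary analysis will be based on results from imaging studies and clinical data confirmed by Independent Central Review".

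On masking there are two statements. Section 3.5.2 says of the designated radiologists, just before the adjudication sentence: "They will be blinded to the local radiology findings". Section 2.6 says that "tumor response of each patient will be reviewed by independent radiologists and oncologists in a blinded fashion".

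On reporting, section 5.9 says: "Both investigators reported and independently adjudicated outcomes will be reported". The protocol describes no tabulation of discordant cases and no ORR based on the first independent reader alone.

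**The concern.** The primary ORR is offered as an independently reviewed figure, in a study that section 5.1 calls pivotal for approval in Japan and South Korea. Some of the radiology results inside it may nevertheless be site readings. The site differs from the central reader in that it manages the patient: under 2.6, local radiology and clinical judgement guide its decisions on treatment.

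The adjudicator has only two candidates, and one of them is the blinded first read. Adjudication can therefore move a patient's radiology result only towards the site. If the adjudicator also knows which reading is the site's, the choice may be influenced by its source, and the text leaves that open.

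At stake is how far the primary result depends on site readings. Nothing in the planned reporting would show this.

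**Working it through.** **1. What adjudication can do to responder status**

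| Site | First reader | Final radiology status |
|---|---|---|
| Responder | Responder | Responder; status not in dispute |
| Non-responder | Non-responder | Non-responder; status not in dispute |
| Responder | Non-responder | First reader's, or changed to responder (the site's) |
| Non-responder | Responder | First reader's, or changed to non-responder (the site's) |

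Differences in category (CR against PR) or in dates also go to the second radiologist, but they do not move the ORR.

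**2. What the planned parallel reporting shows**

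Consider imaging results only, and write:
- F = responders by the first reader
- A = patients whom the site calls responders and the first reader does not; a = those among A resolved to the site
- B = patients whom the first reader calls responders and the site does not; b = those among B resolved to the site

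Then:
- Site count = F + A − B
- Adjudicated count = F + a − b
- Reported gap = (A − a) − (B − b)

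A gap of zero arises if there was no discordance at all (A = B = 0). It also arises if every discordant patient was resolved to the site (a = A, b = B). The gap therefore does not identify a or b. Only F, or a table of discordant cases, does. The outcomes reported under 5.9 also include skin and clinical data added at oncologist review, which blurs the comparison further.

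**3. The masking statements side by side**

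Section 3.5.2 blinds the radiologists to local findings and then has one of them choose between the local finding and another. The two sentences are compatible if both readings are shown without labels. No sentence says that they are.

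**4. When one patient matters**

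Inputs from section 5.2: N = 40, assumed ORR 30%, reference rate 10%, two-sided alpha 5%, stated power 89%. Section 5.9 specifies exact 95% intervals.

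The plan's own figures come first:
- The stated interval is the normal approximation: 0.30 ± 1.96 × √(0.30 × 0.70 / 40) = 0.30 ± 0.142, or 15.8% to 44.2%. It agrees.
- Power, exact binomial: P(X ≥ 9 | 40, 0.30) = 0.889, matching 89%. The neighbouring cuts do not match: P(X ≥ 8) = 0.945 and P(X ≥ 10) = 0.804.
- At a true 10%, P(X ≥ 9) = 0.0155 and P(X ≥ 8) = 0.0419. So 9 is the smallest count with one-sided error of at most 0.025.

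The protocol writes no success rule; 9/40 is inferred from the power statement.

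Exact (Clopper–Pearson) limits are the 0.025 quantile of Beta(x, 41 − x) and the 0.975 quantile of Beta(x + 1, 40 − x):

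| Responders | ORR | Exact 95% CI |
|---|---|---|
| 8/40 | 20.0% | 9.1–35.6% |
| 9/40 | 22.5% | 10.8–38.5% |
| 12/40 | 30.0% | 16.6–46.5% |

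Each patient is 1/40 = 2.5 points. Between 8 and 9, one patient decides whether the lower limit clears 10%. From the planned 12/40, a net change of 12 − 8 = 4 patients would be needed to fall below the cut.

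Chance that the count is 8 or 9:
- True ORR 30%: 0.0557 + 0.0849 = 14.1%
- True ORR 10%: 0.0264 + 0.0104 = 3.7%

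**The case against.** The strongest reply is that every deciding step is independent. A discordant site reading enters only if an independent radiologist prefers it, and independent oncologists then assign the response themselves. In a single-arm trial the central readers also know that every patient is treated, so knowledge of treatment does not separate them from the site. This stands as a limit on the concern. It does not change the fact that the adjudicator's only alternative to the blinded read is the site's.

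A second reply is that blinding is stated twice and can be read as covering unlabelled presentation. That is fair: the gap is one of wording. A review charter, or the separate SAP that 5.1 refers to, might close it, but neither text is in the document reviewed.

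Third, the 9/40 cut is inferred, the analysis is called primarily descriptive, and the primary count is fixed only after oncologist review. The PPS also includes patients with clinical progression in Cycle 1 and no imaging, whom radiology adjudication cannot move. All of this stands, so the boundary figures are context and do not estimate an effect.

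A reader might infer more: that adjudication is unmasked, that the ORR is inflated, or that a fresh blinded third read is required. The documents support none of these. Masking is unstated, which does not show that it is absent. The site could undercall as well as overcall, and no discordance rates are given. On responder status a fresh read would still have to agree with one side, so it gains little over masked selection. It would also take response and progression dates from a third reading.

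**Conclusion.** The point holds in limited form. The rule in 3.1.1 and 3.5.2 allows a site reading to replace the blinded read as the radiology result behind the primary ORR. Source masking at that step is not stated, and the planned parallel reporting cannot show how many site readings were adopted or in which direction they moved the figure.

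The size and direction of any bias cannot be derived from the documents. A single adopted reading changes whether the exact lower limit exceeds 10% only at the boundary between 8/40 and 9/40. That rests on 40 evaluable patients and on a cut inferred from the 89% power. The change is worth making because it is cheap and tests how far the primary figure depends on the site.

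**What to change.** **(a) In any case, from existing readings.** Report the number of patients discordant on responder status, by direction, and how each was resolved. Add a sensitivity ORR with exact 95% CI that uses the first blinded reader's result throughout. Label it imaging-only and place it beside the adjudicated imaging-only ORR, with the same patients in both, so that the difference reflects adjudication and not the skin or clinical data added later.

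**(b) Depending on stage.** If adjudication is not complete, amend 3.1.1 and 3.5.2 so that the second radiologist sees the two readings without source labels and in random order. If it is complete, do not re-adjudicate; state in the report whether the adjudicator was masked to source.

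**Cost.** Part (a) is one extra table and needs no new reads. Part (b) needs no extra reader or scans. If adjudication is still open, it takes a short amendment with IRB/IEC review as local rules require (5.1, 6.1), across a planned 25 + 10 = 35 to 35 + 15 = 50 sites. Last patient in was planned for 3Q 2018, and 5.1 requires the independent reviews to finish before the main analysis. At version 6.0 (July 2021) the table and the statement on masking may be all that can still be done.
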